6.10 COMPLIANCE ASSESSMENTS

Tablet adherence: Will be assessed by site staff at each visit by the simple structured questionnaire. This will allow to monitor safety and maintain blinding of central trial staff.

Participants who stop all of their trial-allocated IMP for more than four weeks and so not restart the IMP will be classed as non-compliant.

Participants will be asked to return any packs of unused tablets to the local community pharmacy (or hospital pharmacy if more convenient) at the end of their participation in the trial. All returned tablets will be destroyed.

6.11 LONG TERM FOLLOW UP ASSESSMENTS

Participants will not be followed up long term after the end of the treatment period. Participants who consented at enrolment to further contact for future research may be contacted as new research opportunities arise.

6.12 STORAGE AND ANALYSIS OF SAMPLES

Full blood count, urea and electrolytes and renal function will be analysed and stored as a part of the standard clinical care according to the routine NHS methods.

7. DATA COLLECTION

Section 7.2 (study assessments) details data to be collected, including time points and who will collect data.

7.1 SOURCE DATA DOCUMENTATION

Source data is defined as all information in original records and certified copies of original records or clinical findings, observations, or other activities in a clinical trial necessary for the reconstruction and evaluation of the trial. Source data are contained in source documents.

Source documents are original documents, data and records where source data are recorded for the first time.

Study data will be recorded on source documents (patient's paper and electronic medical records), trial documents (signed consent and completed follow-up questionnaires) and on study specific CRFs (paper and electronic).

The Source Data Plan will specify the location where all the trial data points are documented for the first time and how investigators will report and record study data into CRFs.

If the study data is first collected on a paper trial document, such as completed consent or paper CRFs, investigators must file all the completed documents in the ISF. If the study data is entered directly into electronic CRFs, the CRF will act as the source for the specified study data points.

The Source Data Plan must be completed before each site activation.

7.2 CASE REPORT FORMS

The electronic case report forms (eCRF) will be used to collect trial data. The web-based trial database will require user authentication with user-specific access rights for data entry, editing, and password protection. A separate database will be used to encrypt and store participants' personal identifiable data required to perform the follow-up. Paper versions of the

eCRF will assist with data collection when interviewing patients at baseline and during followup visits by phone or post. Research staff will file all completed paper CRFs in the ISF or TMF if data have not been entered directly on e-CRF.

Section 7.2 (study assessments) details data to be collected, including time points and who will collect data.

Baseline case report forms will include pre-randomisation and post-randomisation data collection.

Baseline eCRFs will contain:

- General eligibility criteria confirmation
- Cilostazol eligibility criteria confirmation
- ISMN criteria confirmation
- Investigator confirming eligibility and their role
- Informed consent details (date of the ICF, date of PIS given to participant, version of PIS and ICF, Investigator taking consent details and their role)
- Participant details (initials, date of birth, sex assigned at birth, ethnicity, years of fulltime education and occupation, employment status)
- Medical history (details of incident stroke, past medical history, vascular risk factors, concomitant medications and the characteristics of the lacunar stroke and SVD features on brain imaging.
- Medication list
- Lifestyle risk factors (smoking cigarettes and alcohol use)
- Falls
- Blood pressure, weight, and height
- Quality of life (5D-5L/ EQ-VAS)
- Cognitive testing (MOCA, Trail Making Test B, concentration MMSE)
- Participant contact details (name, postal address, telephone, email)
- Participant CHI/NHS Number
- GP contact details (name
- Optional: Participant close personal contact details to be used when the participant is uncontactable during follow-up (name, postal address, telephone, email, relationship)
- Date and time of randomisation

The participant, GP, and participant's CHI/NHS Number will be encrypted and be stored separately from the anonymised trial data in compliance with data protection regulations. The nominated close personal contact details collected on the paper Contact form will be stored securely only at the local hospital NHS research team.

Prescription eCRF will include:

- Date of prescription
- Duration of prescription (3 or 6 months)
- Tables dispensed (name of the drug and dose)
- Brand

Follow-up CRFs will include:

- Week 1-2 telephone follow-up form completed by the local site team:
 - Status of the participant (available, lost to follow-up, declined, withdrawn, died)
 - IMP symptoms
 - IMP compliance
 - Blood pressure
 - Outcome and safety events

•

- Week 3-4 telephone follow-up form completed by the local site team:
 - Status of the participant (available, lost to follow-up, declined, withdrawn, died)
 - IMP symptoms
 - IMP compliance
 - Blood pressure
 - Outcome and safety events
 - **Month 6** telephone follow-up completed by the local site team:
 - Status of the participant (available, lost to follow-up, declined, withdrawn, died)
 - IMP compliance
 - Blood pressure
 - Medication list
 - Supplements
 - Outcome and safety events
 - Details of the investigator who completed the phone questionnaire
- Month 6 postal follow-up completed by the central blinded trial co-ordinators:
 - Status of the participant (available, lost to follow-up, declined, withdrawn, died)
 - Type of accommodation
 - Vascular events
 - mRS
 - Smoking cigarettes and alcohol use
 - IMP symptoms
 - Falls
 - Stroke Impact Scale
 - Quality of life (5D-5L/ EQ-VAS)
 - Details of the person who completed the postal questionnaire
- Month 6 telephone follow-up completed by the central blinded trial co-ordinators:
 - Status of the participant (available, lost to follow-up, declined, withdrawn, died)
 - tMOCA
 - TICS-M
 - Concentration (MMSE)
 - Animal naming
 - Zung (mood)
 - Outcomes and safety events
- Month 12 telephone follow-up completed by the local site team:
 - Status of the participant (available, lost to follow-up, declined, withdrawn, died)
 - IMP compliance
 - Blood pressure
 - Medication list
 - Supplements
 - Outcome and safety events
 - Details of the investigator who completed the phone questionnaire
- Month 12 postal follow-up completed by the central blinded trial co-ordinators:
 - Status of the participant (available, lost to follow-up, declined, withdrawn, died)
 - Type of accommodation
 - Vascular events
 - mRS
 - Smoking cigarettes and alcohol use
 - IMP symptoms

- Falls
- Stroke Impact Scale
- Quality of life (5D-5L/ EQ-VAS)
- Details of the person who completed the postal questionnaire
- Month 12 telephone follow-up completed by the central blinded trial co-ordinators:
 - Status of the participant (available, lost to follow-up, declined, withdrawn, died)
 - tMOCA
 - TICS-M
 - Concentration (MMSE)
 - Animal naming
 - Zung (mood)
 - Outcomes and safety events
- **Month 18** telephone follow-up completed by the local site team:
 - Status of the participant (available, lost to follow-up, declined, withdrawn, died)
 - IMP compliance
 - Blood pressure
 - Medication list
 - Supplements
 - Outcome and safety events
 - Details of the investigator who completed the phone questionnaire
- Month 18 postal follow-up completed by the central blinded trial co-ordinators:
 - Status of the participant (available, lost to follow-up, declined, withdrawn, died)
 - Type of accommodation
 - Vascular events
 - mRS
 - Smoking cigarettes and alcohol use
 - IMP symptoms
 - Falls
 - Stroke Impact Scale
 - Quality of life (5D-5L/ EQ-VAS)
 - Health economic parameters
 - Employment status
 - Details of the person who completed the postal questionnaire
 - Month 18 telephone follow-up completed by the central blinded trial co-ordinators:
 - Status of the participant (available, lost to follow-up, declined, withdrawn, died)
 - tMOCA
 - TICS-M
 - Concentration (MMSE)
 - Animal naming
 - Zung (mood)
 - Outcomes and safety events

Follow-up data will be collected on paper and electronic CRFs. If a participant needs help completing the follow-up questionnaires due to, e.g., visual or hearing impairment, a carer or relative may assist with it, and it will be recorded on the e-CRF. **Outcomes and Serious Adverse Events CRF** will include any clinical trial outcome reported from the moment of randomisation until the last follow-up at 18 months and any SAE reported from randomisation until up two weeks after the last dose of IMP is administrated.

Outcome events will be reported on the e-CRF and reviewed by the members of the trial management group. The event adjudication process will include checking for duplicates as

reported events may come from several sources (site research team, participant, follow-up questionnaire, GP or carer, friend, or relative). The relevant clinical, radiographic or pathological information about the reported event will be obtained from the site hospital research team, e.g., Outpatient clinic letter, Discharge summary, brain imaging and radiological report, and blood results. Patient identifiers will be redacted from these documents before sending for internal adjudication to confirm if the event is classified as the outcome. Any potential SAEs or SUSARS identified during the review process will be reported to the sponsor using online e-CRF.

The anonymised **brain scans** that diagnosed the qualifying lacunar stroke and any reported clinical outcomes will be stored in a separate imaging database described in section 8.3. The central research staff will check each brain scan to confirm that it relates to the correct participant, correct time of the event, includes the required imaging sequences, does not show other explanations for the symptoms and will make scan available for the readers.

All case report forms must be reviewed and approved by the ACCORD Monitor prior to use (see ACCORD SOP CR013 CRF Design and Implementation).

NOTE: All electronic case report forms are subject to Co-Sponsor approval (see section 8.3).

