Note that randomisation will be performed during normal office hours (09.00 - 17.00) and the trial allows for randomisation to occur any time beyond 24hrs after the stroke (if the eligibility criteria are met) with no upper time limit after the stroke. Therefore, in the event of computer failure (for example: server failure), the investigator will wait until the computer system is re-established to perform the randomisation. Normally, this would only be a few minutes to two hours. However, if this delay requires the patient to return on a separate occasion to collect the drugs, then a separate appointment will be made and the patient's travel expenses covered as per other trial visits or the drug supply may be sent by post for the next day delivery.

Patients will be randomised to one of the following at a 1:1 ratio as per Section 6.3:

- cilostazol versus no cilostazol
- ISMN versus no ISMN

resulting in a partial factorial comparison of cilostazol versus ISMN versus both drugs versus neither drug.

All participants will continue their usual prescribed guideline stroke prevention medication.

The randomisation algorithm will allocate a unique participant identifier which will be used to label the treatment pack containing the appropriate drug made up for the patient and dispensed by the local Pharmacy.

Participants with an indication for or contraindication to one of the trial drugs may still be randomised to the other trial drug. If a participant allocated to both trial drugs develops a contraindication to one of the trial drugs after randomisation into the trial, then they should discontinue that drug but continue to take the other trial drug. If a patient has to discontinue either or both drugs, they should continue to be followed up in the trial as planned (unless they withdraw from the trial). Patients should remain in follow up until the end of the trial follow up period, even if they discontinue trial drug, unless they withdraw from the trial. Drug discontinuation will be recorded.

The study will be performed open label. Placebo tablets are not available and masking by encapsulation is too complicated and expensive. However, blinding of outcomes is important to obtain unbiased information about tolerability, safety, and efficacy. As such, IMP adherence structured questionnaire and prescribed medications will be taken by site staff who are already unblinded to trial allocation, while ascertainment of the main cognitive and

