6.8 SAFETY ASSESSMENTS

Safety assessments for the trial drug will occur at 2-weekly intervals in the first month after randomisation and six-monthly intervals thereafter during the 18 months duration of the trial.

The local hospital sites will ask participants by phone about the presence of symptoms that might be related to taking the trial drugs (e.g., headache, bleeding) during the first month after randomisation
The central blinded trial co-ordinators will continue to ask participants about the IMP symptoms as a part of the postal questionnaire at 6, 12 and 18-months follow-up visits.

The local hospital sites will phone-visit participants at 2-weekly intervals in the first month, and at 6, 12, and 18-month follow-up visits to ask about adherence to trial medication.

Investigators from the local hospital sites and central trial co-ordinators will record and report the outcome and safety events including SAEs, SARs and SUSARs between randomisation and the last follow-up visit at 18 months based on the information from the follow-up questionnaires as well as alerts from the hospital records. The safety reporting will include two weeks after the last dose of IMP is administrated.

The IMP symptoms, drug adherence, outcome, and safety events will be recorded in the eCRF. The SAEs, SARs and SUSARs will be reported to the sponsor.

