Drugs symptoms: Will be assessed by site investigators after randomisation at 1-2 weeks and 3-4 weeks visits and by the blinded central team at 6, 12 and 18 months using a short simple validated questionnaire to assess for symptoms potentially related to trial tablets as part of safety monitoring, including headache, dizziness, palpitations, altered bowel habit, falls, bruising and bleeding, as in LACI-2. The participant will be asked whether any symptoms were severe enough to interfere with normal daily activities. Participants will also be able to report any other symptoms and describe them in detail.

Drug adherence: Will be assessed by site investigators at each follow-up visit by phone. Participants will be asked about adherence to medication using a very short structured question. These contacts will be timed around prescribing for the next batch of IMP.

Blood pressure: Will be collected by the site hospital teams as a part of the baseline visit. BP measurements, if available, will be collected by sites as a part of the site phone follow-up at each follow-up visit. Sites can use self-recorded BP by the participant using their own BP monitor or self-reported from routine GP or other hospital measure. The medication list including antihypertensive drugs will be collected at each visit by the hospital team as a part of the data collection on the continuing routine stroke prevention therapy.

Health economics: EQ-5D-5L, EQ-VAS will be collected at 6, 12 and 18 months and measures to assess health economic usage and impact of trial drug (contact with health care, place of residence, return to work, etc) will be collected centrally at 18 months.

Repeat Brain CT or MRI: any repeat scanning performed to assess a recurrent neurological event during the trial will be anonymised and sent to Edinburgh for central blinded adjudication.

Follow-up:

After randomisation, all participants will be followed up for outcome and safety events until the end of their follow-up at the 18 months visit.

The follow-up includes five visits. Participants will be followed up remotely by phone and post for 18 months by two teams: the local site and the central research team. Each time, a questionnaire will be completed by a participant by telephone or on paper or both to collect trial outcomes.

Local site:

- Contact at one-two and three-four weeks by phone to advise on dose escalation, check symptoms and drug adherence, BP, outcomes and safety.

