10. PHARMACOVIGILANCE

The Investigator is responsible for the detection and documentation of events meeting the criteria and definitions detailed below.

Full details of contraindications and side effects that have been reported following administration of the IMP can be found in the relevant Summary of Product Characteristics (SPC) Booklet for cilostazol and isosorbide mononitrate.

Participants will be instructed to contact their Investigator at any time after being randomised if any symptoms develop. All adverse events (AE) that occur after randomisation until death or completion of active trial follow-up (two weeks after the last dose of IMP is administrated) must be recorded in the Case Report Form (CRF) or AE log. In the case of an AE, the Investigator should initiate the appropriate treatment according to their medical judgment.

The main factor in assessing the safety of cilostazol and isosorbide mononitrate is the collection of the trial secondary outcomes:

- recurrent ischaemic stroke
- TIA
- major systemic or brain haemorrhage
- fatal or non-fatal MI
- death of any cause
- dementia.

These outcomes should be reported as trial outcomes in the e-CRF and are exempt from the safety reporting as SAEs. Any other adverse events that fulfil the seriousness criteria of the adverse event should be reported as SAE to the Sponsor.

Both cilostazol and isosorbide mononitrate have a known safety profile. The IMP symptoms that are not serious adverse reactions (AR), such as headache or loose stools, will be collected and reported on the e-CRF at each follow-up visit. The SARs and SUSARs will be reported to the Sponsor.

CR007-T01 v9.0 Page **50** of **67**

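### The protocol contradicts itself on when AE and SAE collection ends, and the dose-tied end cannot be applied to the arm given neither drug

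*Protocol*

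**What the plan says.** Two places tie the end of collection to dosing. Section 7.2 describes the form for outcomes and SAEs. In one sentence it takes trial outcomes to the last follow-up at 18 months but takes "any SAE reported from randomisation until up two weeks after the last dose of IMP is administrated". Section 10 requires AEs up to death or "completion of active trial follow-up (two weeks after the last dose of IMP is administrated) must be recorded".

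Other places use the calendar. Section 6.8 has sites and the central team record "safety events including SAEs, SARs and SUSARs between randomisation and the last follow-up visit at 18 months", then adds: "The safety reporting will include two weeks after the last dose of IMP is administrated". Section 6.9 states that "all participants will be followed up for outcome and safety events until the end of their follow-up at the 18 months visit". Section 5.5.1 says: "Patients should remain in follow up until the end of the trial follow up period, even if they discontinue trial drug". Section 5.6 lets a participant withdraw from medication alone while safety data are still collected.

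Three further provisions matter. There is no placebo (section 6.2), and the dosing table for participants allocated neither drug is nil throughout (section 6.3). Section 9.2 analyses SAEs, SARs and SUSARs not already counted as outcomes by binary logistic regression, with all analyses by intention to treat. Section 10 exempts recurrent ischaemic stroke, TIA, major systemic or brain haemorrhage, MI, death and dementia from SAE reporting and records them as trial outcomes.

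**The concern.** A yes/no analysis of who had an SAE is a fair randomised comparison only if every arm is observed over the same window. A window that closes two weeks after the last dose closes early for someone who stops active drug. It has no closing date for someone never given drug. A site following sections 7.2 and 10 could properly stop recording SAEs in an early stopper while recording them to month 18 in a control. A site following sections 6.8 and 6.9 would go on recording in both.

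The events at stake are the SAEs that are not trial outcomes, which are the ones section 9.2 compares, and AEs generally. An event that was never recorded cannot be recovered by a later SAP, so this has to be settled in the protocol and the CRF guidance.

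**Working it through.** **The provisions side by side**

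| Section | Collection ends | Usable in the arm given neither drug? |
|---|---|---|
| 7.2 (SAE form) | two weeks after last IMP dose | no |
| 10 (AEs) | death, or two weeks after last IMP dose | only in those who die |
| 6.8 | 18-month visit, with two post-dose weeks included | yes, for the 18-month part |
| 6.9 | 18-month visit, all participants | yes |
| 5.5.1 and 5.6 | follow-up and safety data continue after drug is stopped | yes |

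Section 10 equates the dose-tied end with the end of active follow-up. That cannot be squared with section 5.5.1, which keeps early stoppers in follow-up. A further ambiguity is that section 5.5.1 lets a participant on both drugs stop one and continue the other, and neither dose-tied passage says which last dose counts.

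**Size under the literal wording**

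The protocol states no figure to reproduce, and it gives no stopping rate or SAE rate for LACI-3. The shares and times of stopping below are assumptions.

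Inputs:
- 18 months is taken as week 78, since section 6.3 puts the taper in week 79 and nil in week 80.
- A participant who stops in week t is observed to week t + 2. Stopping at month 3 (week 13) gives week 15.
- The arm given neither drug is assumed to be observed to week 78, because the wording gives it no end.
- Completers on active drug are either capped at week 78 or, taken literally, run to week 79 + 2 = 81.

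For a share s stopping, the ratio of observation time in an active arm to the arm given neither drug is:
- capped: r = [s × (t + 2) + (1 − s) × 78] / 78
- uncapped: r = [s × (t + 2) + (1 − s) × 81] / 78

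Worked example for s = 0.20, t = 13, capped: (0.20 × 15 + 0.80 × 78) / 78 = 65.4 / 78 = 0.838.

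For ISMN versus no ISMN in the full factorial with equal cells and equal stopping, half of the comparator takes cilostazol. The ratio becomes r / [(1 + r) / 2]. For the same example it is 0.838 / 0.919 = 0.912.

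| Share stopping at week 13 | Active vs neither, capped | ISMN vs no ISMN, capped | Active vs neither, uncapped | ISMN vs no ISMN, uncapped |
|---|---|---|---|---|
| 0% | 1.000 | 1.000 | 1.038 | 1.019 |
| 10% | 0.919 | 0.958 | 0.954 | 0.976 |
| 20% | 0.838 | 0.912 | 0.869 | 0.930 |
| 30% | 0.758 | 0.862 | 0.785 | 0.879 |

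**Direction**

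Uncapped, active completers gain 81 − 78 = 3 weeks. The ratio equals 1 when s = 3 / [81 − (t + 2)]:
- stopping at week 4: 3 / 75 = 4.0%
- stopping at week 13: 3 / 66 = 4.5%
- stopping at week 26: 3 / 53 = 5.7%
- stopping at week 39: 3 / 40 = 7.5%

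Below these shares the active arms are observed for longer than the arm given neither drug, and the distortion runs against the drugs. With one calendar window for all arms the ratio is 1 by construction, before death or loss to follow-up.

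**The case against.** The strongest reply is that most of the protocol already provides 18-month capture. Besides sections 6.8, 6.9, 5.5.1 and 5.6, section 10.2 has participants asked about AEs and SAEs at every visit. The month 6, 12 and 18 forms listed in section 7.2 collect safety events with no condition on being on drug. Section 6.8 words the two weeks as something included, not as a cut-off, and they would fit as an extension over the taper after month 18. The major safety events are outcomes collected to 18 months in every arm. The DMC harm guideline in section 3 concerns intracerebral haemorrhage, systemic bleeding and fatal SAEs, so it is largely protected.

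Much of this stands. A reader might infer from sections 7.2 and 10 that SAE windows do close early for those who stop drug, and that the safety comparison is therefore biased towards the drugs. The documents do not support that. They contradict themselves without settling on the early cut-off, and the direction of any bias depends on the stopping rate. A reader might also take the 84% at 20% stopping to mean that a true SAE excess of 15% to 20% would look neutral. That treats a logistic analysis as person-time and assumes the excess persists after stopping. It also applies only to an active arm against neither drug; for ISMN versus no ISMN the corresponding ratio is about 91%.

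The reply does not remove the contradiction. Section 7.2 sets the outcome window and the SAE window against each other in one sentence, so the SAE clause is hard to read as an addition to 18 months. No reading gives it an end in an arm without a last dose.

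**Conclusion.** Wrong as written, as an internal contradiction that can bias one secondary comparison; bias is not established. Sections 7.2 and 10 conflict with sections 6.8, 6.9, 5.5.1 and 5.6 on when AE and SAE collection ends, and their end point does not exist for participants allocated neither drug.

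The table's range is conditional on the literal wording being followed, on 10% to 30% stopping at month 3, and on controls being observed to 18 months. The figures for ISMN versus no ISMN also assume equal cells and equal stopping on cilostazol alone. If sections 6.8 and 6.9 govern in practice, nothing is shortened. The exposure is confined to AEs and to SAEs that are not trial outcomes.

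**What to change.** Reconcile sections 6.8, 7.2 and 10. For the randomised comparison, state one AE and SAE window that is the same in every arm: from randomisation to the 18-month visit, whether or not drug was stopped.

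State any reporting for two weeks after the last dose in a separate sentence, for pharmacovigilance only, and say which last dose is meant for participants on both drugs. Keep events after the 18-month visit out of the between-arm comparison; otherwise active completers contribute about three weeks that controls do not.

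The cost is an amendment to wording and matching CRF guidance. The site and central contacts at 6, 12 and 18 months already exist for all participants, so no visit or form is added.
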